5.2.8. Statistical methodology

A descriptive analysis will be performed of all the variables recorded for the study population. For the continuous variables, the mean, the SD, the 95% CI of the mean, the median, IQR (P25-P75), min. and max, and valid n will be calculated. Categorical variables will be presented as absolute and relative frequencies (percentages).

For bivariate analysis, continuous endpoints may be compared across subgroups of population using two-sample t-tests or ANOVA (if normality criteria are met), or the Mann–Whitney U test or Kruskal-Wallis test (if normality criteria are not met). The categorical endpoints will be analysed using the Chi-square or Fisher test, as appropriate. If apply, lineal correlations between continuous variables will be analysed (Pearson or Spearman correlations).

Multivariate exploratory analyses (e.g. generalized linear models) will be applied which include costs (Total annual IPF-related costs) and quality of life (SGRQ and EQ-5D-5L in baseline visit-T0) as dependent variables, and the explanatory variables will be discussed based on previous bivariate analyses and clinical relevance with $p<0.1$. Sample size and constraints imposed by the analysis models may prevent to include all variables of interest in this setting.

For all exploratory statistical tests, a significance level alpha of 0.05 will be assumed.

The data analysis will be performed by using the SAS statistical package, version 9.4 or later.

All costs will be estimated per patient per year, and will be specified with respect to the different FVC % predicted level (FVC<50%, FVC 50-80%, FVC>80%) and total sample.

5.2.9. Handling of missing data

Missing values will not be imputed in the main analysis. However, if considering only observed values for an analysis is felt to bias the results post-hoc sensitivity analyses including imputation techniques might be applied.

For each questionnaire, its indications will be followed (for example, calculating the score considering the number of available items or missing all data). A missing response in either of the questionnaires will exclude the patient from the specific analyses.

In context of concomitant medication date in T0, missing data in the month will be imputed as June.

In context of pharmacological and non-pharmacological treatment related to FPI, if the initial treatment date is missing and the treatment is ongoing, the cost corresponding to a full year will be imputed (in case the diagnosis of the PFI is earlier than 2018).

No other missing data will be imputed. If patients have missing values for any other endpoints, these patients will be excluded from the analysis of that endpoint.

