### **9.10.2 Study records**

Case Report Forms (CRFs) for individual patients will be provided by the sponsor via remote data capture. Data will be captured via a web-based Electronic Data Capturing system. The site staff will enter and edit the data via a secure network, with secure access features (username, password and secure identification – an electronic password system). A complete electronic audit trail will be maintained. Patients must not be identified on the eCRF by name. Appropriately coded identification (i.e. Patient numbers) must be used. All patient/caregiver questionnaires will be paper-based and will be left at the site upon completion by the patient.

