5.2.7. Analysis of secondary variables

The following analyses will be performed according to secondary objectives.

1) To estimate the QoL of patients with IPF according to predicted FVC% through the SGRQ and EQ-5D-5L questionnaires and the Barthel index

Health-related quality of life (QoL) will be investigated with the St George's Respiratory Questionnaire (SGRQ) and the EQ-5D-5L questionnaire. Quality of life will be assessed at visits T0, T6 and T12.

The **St. George's Respiratory Questionnaire (SGRQ)** is a 50-item questionnaire developed to quantify the impact of the disease on the health and QoL perceived by patients with respiratory diseases. It consists of 50 items divided into 3 scales: symptoms (frequency and severity of respiratory symptoms), activity (activity limitations due to dyspnoea) and impact (psychological and social functioning disorders caused by the disease). The final scores range from 0 (fewest limitations) to 100 (most limitations). Spanish validated version will be used.

For the **SGRQ**: mean, SD, 95% CI of the mean, median, IQR (P25-P75), max. and min. will be calculated from the scores obtained on the three scales (symptoms, activity, impact) and from the total score in the total population and in each subpopulation (FVC <50%, FVC 50-80%, FVC >80%).

The **EQ-5D-5L** consists of a questionnaire and a visual analogue scale (EQ-VAS). The EQVAS is a self-rated health status using a VAS (0-100). The EQ-VAS records the subject's perceptions of their own current overall health. The self-assessment questionnaire is self-reported description of the subject's current health in 5 dimensions i.e., mobility, self-care, usual activities, pain/discomfort and anxiety/depression. The subject is asked to grade their own

current level of function in each dimension into one of five degrees of disability (no problems, slight problems, moderate problems, severe problems, and extreme problems).

This decision results in a 1-digit number expressing the level selected for that dimension. The digits for 5 dimensions can be combined in a 5-digit number describing the respondent's health state. Spanish validated version will be used.

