Caregivers who have signed the specific written informed consent form will be asked to complete the Zarit Burden Interview. It is a self-report measure. The revised version contains 22 items. Each item on the interview is a statement which the caregiver is asked to endorse using a 5-point scale. Response options, in the spanish version, range from 0 (Never) to 4 (Nearly Always). The final scores range from 0 and 88: Little or no burden (≤ 42), mild to moderate burden (22-40), moderate to severe burden (41-60) and severe burden (≥ 61).

The responses to the 22 items that make up the instrument will be reported, as well as the total score for the questionnaire. The distribution of caregiver burden will be described by means of absolute and relative frequencies (percentages), according to the following categories:

- Little or no burden: Zarit score ≤ 21
- Mild to moderate burden: Zarit score > 21 and ≤ 40
- Moderate to severe burden: Zarit score > 40 and ≤ 60
- Severe burden: Zarit score ≥ 61

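### Does the SAP's questionnaire rule drop a patient for a single blank item, against its own rule on scoring from available items?

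*SAP*

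**What the plan says.** SAP 5.2.9 (Handling of missing data) deals with questionnaires in two consecutive sentences. The first defers to the instructions of each instrument and gives as its example "calculating the score considering the number of available items or missing all data". The second reads: "A missing response in either of the questionnaires will exclude the patient from the specific analyses". The section ends with a rule for everything else: "If patients have missing values for any other endpoints, these patients will be excluded from the analysis of that endpoint".

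The protocol has the same pair of statements in two places. The scoring rule is in 9.7. The exclusion rule is in 9.7.2 a), directly after the paragraphs on the SGRQ and the EQ-5D-5L.

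Two sets of analyses depend on the rule most directly. One is quality of life by FVC level, the first secondary objective, for which SAP 5.2.7 reports three SGRQ scales and a total, and EQ-5D-5L frequencies by dimension. The other is the exploratory multivariate modelling in SAP 5.2.8, with "quality of life (SGRQ and EQ-5D-5L in baseline visit-T0) as dependent variables".

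**The concern.** Neither document defines a missing response. SAP 5.2.7 e) uses the word at item level for the Zarit interview: "The responses to the 22 items that make up the instrument will be reported". If the exclusion sentence is read the same way, one blank removes the patient, although the sentence before it allows a score from the items that were answered.

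The exposure is plausible. Of the SGRQ the SAP says "It consists of 50 items divided into 3 scales", and protocol 9.10.2 says "All patient/caregiver questionnaires will be paper-based", so occasional blanks are likely. The FVC <50% group is expected to hold only 10 to 22 patients, so each needless exclusion would cost precision there. If sicker patients leave more blanks, the remaining sample would also be selected. Two programmers could build different analysis sets from the same text.

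The reach of the word *either* is a further doubt. In the protocol it follows the SGRQ and EQ-5D-5L text. In the SAP it stands in a general section, in a plan that also analyses the Barthel index and the Zarit interview.

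**Working it through.** **1. The two sentences side by side.** The example in the first sentence names two outcomes: score from the items available, or treat the data as missing. The choice belongs to the instrument's own instructions. The second sentence can then state what happens in the second case: with no usable result, the patient is not in that analysis. Read in this order, nothing conflicts. The closing rule of 5.2.9 works the same way for other endpoints, by dropping the patient from the affected endpoint only.

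**2. How far an exclusion reaches.** The exclusion is from the *specific* analyses, which most naturally means those of the questionnaire with the gap. *Either* ordinarily points to two things. In protocol 9.7.2 a) those are the SGRQ and the EQ-5D-5L, and the secondary objective lists these two questionnaires apart from the Barthel index. The rule removes a patient, whereas the Zarit interview is completed by a caregiver. Spill-over from one instrument to another, or to the Zarit, therefore needs a strained reading.

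**3. Size under the strict reading.** Inputs from the documents: 50 SGRQ items (SAP 5.2.7), about 200 patients, and 5% to 11% of them with FVC <50% (SAP 4.2). The plan's figure for that group reproduces: 200 × 0.05 = 10 and 200 × 0.11 = 22.

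The documents give no item-missing rate q, so q is assumed to be 0.1% to 2%.

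- Independent blanks: share of patients with at least one blank = 1 − (1 − q)^50.
- Blanks clustered within patients (beta-binomial, correlation r assumed at 0.05 and 0.4): share = 1 − B(a, b + 50)/B(a, b), with a = q(1 − r)/r and b = (1 − q)(1 − r)/r.

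| q | Independent | r = 0.05 | r = 0.4 |
|---|---|---|---|
| 0.1% | 4.9% | 2.5% | 0.6% |
| 0.5% | 22.2% | 11.7% | 2.9% |
| 1% | 39.5% | 22.1% | 5.7% |
| 2% | 63.6% | 39.4% | 11.1% |

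At q = 1%, patients with no blank:

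| | Independent | r = 0.05 | r = 0.4 |
|---|---|---|---|
| Of 200 | 121 | 156 | 189 |
| Of 22 (FVC <50%, upper) | 13.3 | 17.1 | 20.7 |
| Of 10 (FVC <50%, lower) | 6.1 | 7.8 | 9.4 |
| Confidence interval width, 1/√(share with no blank) | 1.29 | 1.13 | 1.03 |

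**4. What these figures measure.** They count every patient with any blank. The loss at issue is smaller: patients with a blank whose score could still be computed. The documents do not state how many gaps the SGRQ tolerates, so that loss cannot be derived. Each figure is an upper bound under its own assumptions. Under the reading in step 1, no scorable patient is lost.

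**The case for a change.** The best argument for a change is redundancy. If the instrument's instructions already decide when a score is missing, the exclusion sentence adds little, and a programmer who wants it to do some work might apply it to single blanks. The item-level use of the word in the Zarit paragraph lends support. Existing safeguards do not settle the matter either. The first exclusion criterion concerns inability to complete questionnaires, not an occasional blank. The eCRF completeness checks in protocol 9.6 and 9.8 prompt queries but may not recover an answer left blank on paper. Post-hoc imputation is optional.

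Part of this stands: the term is undefined, and the strict reading cannot be ruled out from the words alone. But the sentence has a use without it, since it says that an unusable result is left out and not filled in, in line with the no-imputation rule that opens 5.2.9. The Zarit wording refers expressly to the 22 items; the disputed sentence has no such qualifier. And the strict reading makes the SAP contradict itself in adjacent sentences, which is a reason to prefer the reading that does not.

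**Conclusion.** No change follows. This is a gap in detail that an analyst fills sensibly: score each instrument by its own instructions, and leave a patient out only where the result cannot be obtained. That is consistent with both sentences, and it gives sound estimates for secondary analyses that the plan itself calls exploratory. The primary cost comparison does not depend on the rule.

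The extra loss under that reading is nil. The range of 0.6% to 63.6% arises only under the strict reading. It rests wholly on assumed missing rates and clustering and overstates the avoidable loss, so it does not show that the plan will give a worse result. SAP 5.2.8 also lists the valid n for continuous variables, so an unexpected drop in scored SGRQ forms would be visible in the output.

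The conclusion assumes that the SGRQ instructions do say how to treat blank items. The documents imply this by their example but do not reproduce those instructions.

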
 The eSalud platform is the access portal to the Spanish healthcare costs database set up by Oblikue Consulting. Source: Spanish Health Costs Database: eSalud [Internet]. Barcelona: Oblikue Consulting, S.L. 2007 [date of access]. Available from: <http://www.oblikue.com/bddcostes/>

Proprietary confidential information © 2017 Boehringer Ingelheim International GmbH or one or more of its affiliated companies

Name of company: Boehringer Ingelheim			
Name of finished medicinal product: Not applicable			
Name of active ingredient: Not applicable			
Protocol date: 15 Jun 2017	Study number: 1199-0296	Version/Revision: 1.0	Version/Revision date: Not applicable
Milestones:	
Planned start of data collection: October-2017 Planned end of data collection: May-2019 Planned final study report: September-2019
		

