## **9. RESEARCH METHODS**

### **9.1 STUDY DESIGN**

Descriptive prospective non-interventional multicenter study based on newly collected data of Idiopathic Pulmonary Fibrosis patients followed-up for one year in secondary care settings (Pulmonology Services).

Idiopathic Pulmonary Fibrosis patients who attend to a routine follow-up visit and fulfil inclusion/exclusion criteria will consecutively enrolled by the investigator of each center. Once patients give their informed consent, the investigator will collect in the Case Report Form (CRF) specifically designed for the study, the corresponding sociodemographic, clinical data and healthcare and non-healthcare resource use registered in the medical records and provided by the patients. Also, patients will be invited to complete the study questionnaires in the inclusion visit (T0), approximately at their six month visit (T6) and twelve month visit (T12). Patients will also have a patient diary where collect data (see section 9.4) between follow-up visits along 12 month.

Three visits per patient will be performed as per clinical practice (the closest visit to 6 months or 12 months after baseline). The inclusion period of the study will be from Oct 2017 to April 2018 and the follow-up will be 12 months for each patient and until April 2018 for the last patient.

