## **9.2.3 Study visits**

The visit flow chart list all data collected and indicates with an “x”, the visit when they are collected. All data collected must be supported in the patient’s source documentation.

Visit flow chart and data collection parameters:

	T0 Baseline Visit	T6 6 month visit (+/- 2 month)	T12 12 month visit (+/- 1 month)
Patient Informed Consent	x		
Patient’s informal caregiver Informed Consent (if applicable)	x	x	x
Inclusion / Exclusion Criteria	x		
Date of Birth (Age)	x		
Gender	x		
Employment status (employment and net incomes)	x	x	x
Anthropometric variables (weight, height and BMI)	x	x	x
Date of IPF diagnosis	x		
FVC (ml, %)	x	x	x
FVC % predicted 	x	x	x
FVC rate change by year	x		x
DLCO (mmol/min/kPa)	x	x	x
DLCO % predicted	x	x	x
The Barthel index	x	x	x

Proprietary confidential information © 2017 Boehringer Ingelheim International GmbH or one or more of its affiliated companies

	T0 Baseline Visit	T6 6 month visit (+/- 2 month)	T12 12 month visit (+/- 1 month)
6MWD	x		x
Smoking status 	x	x	x
Environmental and occupational exposures 	x		
Drugs of abuse 	x		
Exposure to drugs associated with pulmonary fibrosis 	x		
Exposure to viral infection with potential association with IPF 	x		
Concomitant diseases related to IPF (lung transplantation included)	x	x	x
pharmacological and non-pharmacological treatments related to IPF	x	x	x
Patient diary review	x	x	x
IPF related resource use: primary and secondary care visits, outpatient visits, emergency visits (primary care and hospital), hospitalizations, ICU with and without intubation, outpatient tests and other examinations, use of transport, use of formal and informal caregiver,		x	x
IPF related resource use: orthopedic material, formal social services, economic aid and structural adaptations.			x
Days off work due to IPF		x	x
Sociodemographic variables for the caregiver (if applicable): age, gender, employment and relationship with the patient.	x		
Work productivity from informal patient's caregiver (if applicable)		x	x
QoL of the patients (SGRQ and EQ-5D-5L questionnaires)	x	x	x
QoL of the informal patient's caregiver (Zarit Burden Interview). If applicable.	x	x	x
Acute IPF exacerbations 	x	x	x
Safety: Adverse Drug Reactions (serious and non-serious), fatal AE, pregnancy	x	x	x

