1.8. STUDY DESIGN

Non-interventional multicenter study based on newly collected data of IPF patients followed-up for one year in secondary care settings (Pulmonology Services). IPF patients will be enrolled in a consecutive manner over a period of 6 month.

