1.12. STUDY CALENDAR

Start of data collection: 29 November 2017

Planned end of data collection: August-2019

Planned final study report: December-2019

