- Economic aid and formal social services (T12, acute exacerbations)
- Structural adaptations (change in the structure of housing, elevators on the stairs in common areas, complementary technical aids, vehicle adaptation, other) (T12, acute exacerbations).

Calculation of direct health costs

Visits: The cost of visits will be calculated by multiplying the number of visits (emergency, medical) by the corresponding unit cost, which will depend on the health care area (primary or secondary) in which the visit occurred.

Hospitalizations: To calculate the cost of hospitalizations, days of stay in each unit (ICU, ward) will be multiplied by the unit cost corresponding to each unit. The sum of the costs of each service will then be calculated. In addition, emergency room admission will be added: if length of emergency stay was “less than 24 hours”, emergency room visit cost will be considered; if length of emergency stay was “more than 24 hours”, one day of emergency stay cost will be considered. Data on intubation during hospitalization (yes/no) will be used as qualitative information and not calculated as a cost.

Outpatient tests and non-pharmacological treatment: The cost of outpatient tests and non-pharmacological treatment will be obtained by multiplying the natural units of resource use (number of tests) by the unit cost of each outpatient test.

Pharmacological treatment: The costs of pharmacological treatment will be calculated taking into account:

- **Pharmacological doses**

The total dose prescribed of each active ingredient during the last 6 months will be calculated by multiplying the dose prescribed by the time on treatment. The time on treatment will be determined according to the start and end date of treatment. The scheduled dose may be daily, twice a day, three times a day, alternate days, weekly, every 2 weeks, monthly or on demand. If the schedule dose is ‘*on demand*’ an average dose according to the technical data sheet will be calculated.

The calculations described above will provide the total dose that each patient has received for the observational period.

- **Costs**

For treatments dispensed in the pharmacy office, the unit costs for each treatment were calculated taking into account the retail price (RRP) plus value added tax (VAT). From the National Health System (NHS) perspective, the co-payment of the Spanish Royal Decree-Law 16/2012 will be applying:

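### The June rule for a missing month in T0 medication dates has no cap at the T0 visit, so on the planned calendar a drug recorded as started in 2018 is dated after the visit that recorded it (minor)

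*SAP*

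**What the plan says.** SAP 5.2.9 leaves missing values unimputed in the main analysis, with two exceptions for dates.

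- **June rule.** "In context of concomitant medication date in T0, missing data in the month will be imputed as June". It has no condition tied to the visit. It does not say whether the date is a start or a stop date, and it names no day of the month.
- **Full-year rule.** For drug and non-drug treatment of IPF, a missing start date with treatment ongoing leads to a full year's cost, provided IPF was diagnosed before 2018.

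The section then rules out any other imputation.

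On the calendar, Protocol 9.1 says "The inclusion period of the study will be from Oct 2017 to April 2018". SAP 1.12 gives "Start of data collection: 29 November 2017" and SAP 1.8 says "IPF patients will be enrolled in a consecutive manner over a period of 6 month". The planned end of data collection is May 2019 in the protocol abstract and August 2019 in SAP 1.12.

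On costing, SAP 5.2.5 multiplies prescribed dose by time on treatment: "The time on treatment will be determined according to the start and end date of treatment".

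**The concern.** A mid-year month is an ordinary convention for a partly missing date, provided the imputed date is still possible. Here the planned T0 visits in 2018 all fall in the first five months of the year. A drug noted at one of them as begun in 2018 must have started between January and the visit, yet the rule dates it in June. The dataset would then hold baseline medication that begins after baseline. Any derivation that compares start date with T0, such as a flag for treatment at baseline or a duration of prior treatment, would misclassify the drug or return a negative value.

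A second question is whether the same rule reaches the primary outcome. Drug cost depends on start and end dates, so a start moved to June 2018 would fall inside follow-up and remove treatment time that the patient actually had.

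**Working it through.** **1. Reproduce the planned calendar.**

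- Protocol: last T0 on 30 April 2018 + 12 months + the 1-month visit window = 30 May 2019. This agrees with "Planned end of data collection: May-2019".
- SAP: 29 November 2017 + 6 months = 29 May 2018 as the last T0. Adding 13 months gives 29 June 2019. This fits within "Planned end of data collection: August-2019" with about two months to spare.

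**2. Compare each possible 2018 T0 day with an imputed date in June 2018** (1, 15 or 30 June, since no day is stated).

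| Calendar | 2018 T0 days | Days before the imputed date |
|---|---|---|
| Protocol, to 30 April 2018 | 120 | 120 (100%) for all three dates |
| SAP, to 29 May 2018 | 149 | 149 (100%) for all three dates |

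The gap between visit and imputed start runs from 3 days (29 May to 1 June) to 180 days, about six months (1 January to 30 June).

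**3. Visits and years not affected.** T0 visits from October to December 2017 all come after June 2017, so a 2017 start imputed as June stays before the visit. The same holds for any earlier start year.

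**4. Sensitivity to overrun (assumption).** Counting back from 31 August 2019 by 13 or 12 months would allow T0 visits up to 31 July or 31 August 2018.

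| Last T0 assumed | 2018 T0 days | Before 1 June | Before 15 June | Before 30 June |
|---|---|---|---|---|
| 31 July 2018 | 212 | 71.2% | 77.8% | 84.9% |
| 31 August 2018 | 243 | 62.1% | 67.9% | 74.1% |

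These are shares of calendar days, not of patients. With overrun the problem holds for most rather than all such records.

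**5. Conditional effect on cost.** Suppose the June rule were applied to a costed IPF treatment that is ongoing at T0 and continues through follow-up, with a start imputed at the beginning of June.

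- T0 in early January: about 5 months lost, 5/12 = 42% of that drug's year, leaving 7/12.
- T0 in early April: about 2 months lost, 2/12 = 17%, leaving 10/12.
- Full-year rule, where its conditions are met: 12/12.

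One record could thus be costed at 7/12 or 12/12 of a year, depending on whether a date that lacks only its month counts as missing. The SAP does not say.

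**The case against.** **The cost pathway is not in the text.** This is the strongest objection. The June rule names concomitant medication, IPF treatments have their own adjacent rule, and SAP 5.2.5 lists the costed drugs as those due to IPF, collected at T6, T12 and exacerbations. No sentence feeds the June rule into time on treatment. A reader might infer that the primary cost is biased downwards. The documents do not establish that. They do not exclude it either. The flow chart in Protocol 9.2.3 has no separate item for concomitant medication at T0. The dated-treatment item it does list is treatment related to IPF, and exposure to fibrosis-associated drugs is recorded only as yes, no or unknown. What the June rule covers is therefore unclear.

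**Stronger inferences to avoid.**

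- A loss in euros per patient: neither document gives a drug price, and an antifibrotic is an IPF treatment, for which the full-year rule may apply and would not remove time.
- Stop dates pushed past T0: the SAP says only date and does not say that stop dates are covered.
- Newly treated patients undercounted most: this needs both the cost pathway and the distribution of missing months, and neither is given.

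**The last T0 date is derived.** The SAP margin is only three days, and the August 2019 end leaves room for later enrolment. This stands, and it limits the word all to the planned calendar.

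**Few records are involved.** This is probably so. A record needs a 2018 start, a known year and an unknown month, and the eCRF checks in Protocol 9.6 and 9.8 should reduce missing months. Those checks act at data entry, however, and do not correct a date imputed at analysis.

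**Conclusion.** Wrong as written, minor. On the planned enrolment dates in either document, any medication recorded at a 2018 T0 visit as started in 2018 with the month missing receives a start date after that visit. If enrolment overran into summer 2018, this becomes most such records (62–85% of possible T0 days). No other sentence in the SAP corrects it.

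The certain effect is an impossible date order in the baseline medication data. An effect on drug cost is conditional on the rule being used for costed IPF treatments, and its size cannot be given because the number of affected records is unknown. The separate weakness is that two adjacent rules can be read as covering the same IPF record with different results.

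The conclusion assumes that the imputed date is a start date, which is the natural reading but is not stated, and that enrolment followed the planned period.

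**What to change.** Replace the June rule in SAP 5.2.9 with:

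> *If the month of a medication start date at T0 is missing, June is imputed, unless that falls after the T0 visit; in that case the midpoint between 1 January of that year and the T0 date is imputed. A treatment recorded as ongoing at T0 is counted as taken from T0 onwards.*

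Then add a sentence on scope: an IPF treatment with a known start year but missing month follows this rule, and the full-year rule applies only when the start date is wholly missing. Without that sentence, one record could still receive two different costs. State the day of the month used with June, so that the rule can be programmed without a further choice.

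The cost is a few sentences in SAP 5.2.9 and a short change to the date derivation. No new data are needed, and the rule works whether or not enrolment overran.
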